9.2 Data Analysis

Data will be summarized using descriptive methods. Parametric data will be analyzed between groups using unpaired t tests or Mann Whitney U, as appropriate. Rankings of pruritus and PONV will be coded as none-mild vs. severe and Chi-squared and Fishers' Exact tests will be used to compare these outcomes between groups. Significance will be accepted at the 5% level.

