Study Title: A randomized, double-blinded, placebo-control trial of IV ondansetron to prevent pruritus in children who receive intrathecal morphine.
Study Phase: 4
Primary Objective: Demonstrate efficacy of Ondansetron (Zofran) to reduce incidence and intensity of pruritus as a side effect of IntraThecal Morphine (ITM)
Study Design: Prospective, randomized, double-blind, placebo controlled
Study Population: ages 3-17 inclusive
Diagnosis and Main Criteria for Inclusion Each subject must meet the following criteria to be enrolled in this study: Scheduled for any procedure necessitating ITM for pain management. Wt <= 100kg Ability to use verbal or pictorial scoring scales Parental informed consent Subject informed assent, as applicable Subjects who meet any of the following criteria will be excluded from study: Inability to use verbal or pictorial scoring scales (developmental delay) Hypersensitivity to selective 5-HT ₃ receptor antagonists Diagnosed congenital long QT syndrome Severe hepatic impairment Pregnancy and nursing mothers Use of serotonin specific reuptake inhibitors within 14 days Use of serotonergic-nonadrenergic reuptake inhibitors within 14 days Current use of any medications that prolong QT interval
Test Product; Dose; and Mode of Administration: Intervention group: This arm will receive (in a blinded fashion) 0.1 mg/kg of Ondansetron IV diluted in normal saline to a volume of 5 mLs intra-operatively and Ondansetron IV 0.1 mg/kg diluted in normal saline to a volume of 5 mLs every 6 hours for 24 hours postoperatively (not to exceed 40 mg in 24 hours).

Reference or Placebo Therapy; Dose; and Mode of Administration:

Control group:

This arm will receive (in a blinded fashion) a volume-matched placebo (normal saline) intraoperatively as well as IV every 6hrs for 24 hours postoperatively.

Duration of Treatment: Intraoperative time period plus 24 hours from end of surgery.

Statistical Methods:

Data will be summarized using descriptive methods. Parametric data will be analyzed between groups using unpaired t tests or Mann Whitney U, as appropriate. Rankings of pruritus and PONV will be coded as none-mild vs. severe and Chi-squared and Fishers' Exact tests will be used to compare these outcomes between groups. Significance will be accepted at the 5% level.

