1 INTRODUCTION

1.1 Indication

Pruritus is one of the most common and bothersome side effects of intrathecal morphine (ITM) in children, with a reported incidence of 30-70% (1, 2, 13, and 15). We previously found a 40% incidence of pruritus in young children who received intrathecal morphine for major urologic surgery (2) (retrospective review, n= 77, anti-pruritic treatment required in 31 cases). Clinicians, who have witnessed unbearable itching and scratching in their young patients after intrathecal morphine, may be reluctant to offer this effective pain control to future patients, for fear of these unpleasant sequelae.

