1.3 Hypothesis

Pre-emptive and continued blocking of 5HT3 receptors with the 5HT3 receptor antagonist ondansetron, given intravenously prior to ITM and 6 hourly thereafter, will reduce the incidence and intensity of pruritus as a side effect of morphine, in our pediatric patients.

Secondary outcomes to be studied: Post-operative nausea and vomiting and any adverse events.

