2.2 Endpoints

2.2.1 *Primary Endpoint*

Incidence and severity of pruritus within 24 hours post-operatively

2.2.2 *Secondary Endpoint*

- Post-operative nausea and vomiting within 24 hours post-operatively
- Adverse events intra-operatively and within 24 hours post-operatively

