7 ASSESSMENTS

7.1 Primary Endpoint Assessments

For the first 24 hours, subjects will be visited in the PACU, the evening of surgery, the next morning and at 24+/-3 hours (not between the hours of 10p-7a) to obtain the presence and degree of adverse effects, our primary outcomes. Pruritus will be scored similar to previous pediatric studies, as 0 = none; 1 = mild/tolerable/not requiring treatment; 2 = severe/intolerable/requiring treatment (12).

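### The endpoint claims lower incidence and severity of pruritus, but the only test is severe versus none-mild, so the plan cannot confirm that fewer children itch

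*Combined protocol and SAP*

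**What the plan says.** The hypothesis (Section 1.3) is that ondansetron "will reduce the incidence and intensity of pruritus as a side effect of morphine". The synopsis objective has the same two parts, and Section 2.2.1 defines the primary endpoint as "Incidence and severity of pruritus within 24 hours post-operatively". Section 7.1 says that visits are made "to obtain the presence and degree of adverse effects, our primary outcomes", and scores pruritus as "0 = none; 1 = mild/tolerable/not requiring treatment; 2 = severe/intolerable/requiring treatment".

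Section 9.2, repeated in the synopsis, then states: "Rankings of pruritus and PONV will be coded as none-mild vs. severe", to be compared by chi-squared and Fisher's exact tests at the 5% level. The t test and Mann-Whitney U are assigned to parametric data in the sentence before. No section codes the score as 0 versus 1 or more, tests it as an ordinal scale, or defines incidence.

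Section 1.1 gives the sponsor's own 40% incidence and shows how it was counted: "anti-pruritic treatment required in 31 cases" out of 77. Sections 6.2.1 and 7.1 schedule four visits in the first 24 hours. Neither says how four scores, and rescue given between visits, become one value per child.

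**The concern.** Under the planned coding, a child with mild itch and a child with none are the same observation. Presence of itch is measured and is called a primary outcome, but it reaches the analysis only through descriptive summaries. Two things follow.

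- A significant result on the planned test could be reported as lower incidence when all that happened is that severe itch became mild. That would be a real benefit, but not the one that the word incidence suggests to most readers.
- If the sponsor later wants to say that fewer children itched, the test would have to be added after unblinding and would be post hoc.

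The undefined term also appears in Section 10.1, where investigators review the incidence of pruritus by group, with the blind broken, at 20 patients per group. If the cut-point is not fixed before then, it can be chosen with data in view. The missing rule for one value per child leaves a similar choice open: worst score, last score and score at each visit can give different 2x2 tables.

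**Working it through.** **Inputs from the protocol.** 56 per group (Sections 3 and 9.1); 50% decrease (9.1); 31 of 77 treated (1.1); reported incidence 30-70% (1.1); 5% level (9.2). **Assumed.** Two-sided testing, since sidedness is not stated, and the split between none and mild, which the protocol does not give.

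**The plan's own figures.** 31/77 = 0.403, so the 40% is reproduced, as a rate of treatment-requiring pruritus. Halved, it is 20%. The 56 per group is not reproduced from 40% versus 20%: the pooled formula gives 82 per group for 80% power. That is a separate sample-size question, and nothing below depends on it.

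**The planned test at 40% versus 20% severe.** By the pooled normal formula, power = Φ{[0.20√56 − 1.96√(2 × 0.30 × 0.70)] / √(0.24 + 0.16)} = Φ{(1.497 − 1.270)/0.632} = Φ(0.358) = 0.640. Enumerating all pairs of binomial counts gives 0.649 for the uncorrected chi-squared test and 0.573 for Fisher's exact test. Both depend only on the severe rates, so they are the same whatever happens between none and mild.

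**Scenarios.** 400,000 simulated trials each, 56 per group, uncorrected chi-squared. Percentages are none/mild/severe, placebo then ondansetron. In sequence means that both tests are significant.

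| Scenario | Severe test | Any-itch test alone | In sequence |
|---|---|---|---|
| Severe turns mild: 40/20/40 to 40/40/20 | 0.649 | 0.047 | 0.027 |
| Severe turns mild: 30/30/40 to 30/50/20 | 0.648 | 0.051 | 0.030 |
| Only mild falls: 30/30/40 to 45/15/40 | 0.048 | 0.373 | 0.022 |
| Only mild falls: 30/30/40 to 50/10/40 | 0.047 | 0.575 | 0.025 |
| Only mild falls: 30/30/40 to 55/5/40 | 0.047 | 0.763 | 0.026 |
| Only mild falls: 50/10/40 to 55/5/40 | 0.047 | 0.08 | 0.025 |
| Only mild falls: 50/10/40 to 60/0/40 | 0.048 | 0.18 | 0.025 |

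**Both cut-points move together.** The odds ratio implied by 40% to 20% is (0.2/0.8)/(0.4/0.6) = 0.375. Applied to any itch at 50%, the odds are 1 × 0.375 and the rate is 0.375/1.375 = 27.3%. In the same way 60% becomes 36.0% and 70% becomes 46.7%. The any-itch test alone rejects in 0.70, 0.72 and 0.70 of trials. In sequence after the severe test it rejects in 0.58, 0.56 and 0.53.

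**Precision of the any-itch difference.** Half-width = 1.96√(p₁q₁/56 + p₂q₂/56). For 60% versus 36%: 1.96√(0.24/56 + 0.2304/56) = 0.180. For 50% versus 27.3% it is 0.175, and for 70% versus 46.7% it is 0.177.

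**The case against.** The best defence is that incidence already means treatment-requiring pruritus. Section 1.1 calls 40% an incidence and counts it by treatment given, score 2 includes requiring treatment, and Section 9.2 tests score 2. On that reading the severe test is the incidence test, and any-itch counts can be described without a p-value. Much of this stands: the planned split is coherent with the baseline and should remain the primary test. But the protocol does not state the definition, Section 7.1 lists presence separately from degree, and on this reading any itch still has no test.

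Stretching Mann-Whitney to the ordinal score does not help. The text reserves it for parametric data, and an ordinal test would not be a test of score 1 or more versus 0.

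A second objection is that adding a test does little for the case where only mild itch falls. This stands. The sequence confirms such a benefit in about 2-3% of trials. Even alone, an any-itch test rejects in 37-76% if placebo any-itch is 70%, but in only 8-18% if it is 50%; both rates lie within the quoted 30-70%.

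A third is that the difference between 24 hours in Section 6.2.1 and 24+/-3 hours in Section 7.1 is a nominal time and its visit window. That is right, and a reader should not infer a contradiction from it.

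**Conclusion.** The gap is real and moderate. As written, the trial can conclude on severe or treatment-requiring pruritus but cannot confirm that fewer children itch. If severe itch falls from 40% to 20% purely by becoming mild, the planned test is significant in about 65% of trials (57% by Fisher's exact test) with no change in the number who itch. The 40% and the halving come from the protocol; two-sided testing and the none/mild split are assumptions.

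A reader might infer more than this, and the documents do not support it:

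- **That the planned test is wrong or invalid.** It is prespecified and matches the way the 31 of 77 were counted.
- **That the 65% is a false-positive rate.** In that scenario the fall in severe itch is genuine. The error would lie in wording the result as fewer children itching.
- **That a second test would reliably detect a fall confined to mild itch.** It would not, as shown above.

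**What to change.** Amend the synopsis and Sections 1.3, 2.1, 2.2.1 and 9.2, before anyone sees data by group:

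1. Name score 2 versus 0-1 as the primary test. Take each child's worst recorded score over the 24-hour visits, and count post-operative antipruritic rescue as score 2.
2. Prespecify score 1 or more versus 0 as the next test in fixed sequence at 5%. Report its difference and 95% CI whatever the first result.
3. As an alternative to item 2, if the sponsor means incidence to be treatment-requiring pruritus only, define it so and limit the incidence claim to that.
4. Use the same definition in the Section 10.1 interim review.

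Confirm that the CRF records the time of and reason for each antipruritic dose, and that each visit asks about itch since the last one. Section 6.2.1 lists agents used but mentions neither. The reason matters because Section 3 also has diphenhydramine given intra-operatively to prevent nausea and vomiting. No separate rules for the visit window or missed visits are needed for this point.

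**Cost.** Wording and one extra test on scores already collected, possibly with small CRF changes; no extra patients or visits, and no loss of power for the primary test. The protocol should state the downside: the any-itch test is confirmatory only after a significant severe test. The sequence rejects in about 53-58% of trials under the assumed common odds ratio of 0.375 with placebo any-itch of 50-70%. When only mild itch falls, what is gained is mainly the estimate and its interval.

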3 STUDY DESIGN

After obtaining IRB approval and informed consent, we will recruit children ages 3-17 years (able to use verbal or pictorial scoring scales) who are scheduled to intrathecal morphine for a surgical procedure and weigh less than or equal to 100kg.

We will recruit 130 children, and randomize using a random numbers table, stratifying for female gender. The patients who have consented to take part in the study, their families and caregivers, their medical team and the trained observers will be blinded to the treatment being given.

Our proposed ondansetron regime comprises an intra-operative bolus dose of ondansetron, 0.1mg/kg IV, prior to intrathecal morphine injection, followed by around-the-clock ondansetron doses, of 0.1mg/kg IV every 6 hours. We will compare this to a standardized control regime comprising an intra-operative bolus dose of saline placebo and around the clock placebo for 24 hours. 56 patients will comprise each group. All children in both groups will be cared for using a standard, current practice, which includes intra-operative anti-emetics per our departmental algorithm for PONV (Postoperative nausea and vomiting), described below.

Rescue orders for pruritus and PONV are also summarized below. See the attached protocol flowsheet for an overview. Naloxone is routinely ordered, to be given as needed for the treatment of respiratory depression or over-sedation only. We will compare our study group with the control group over the 24 postoperative hours with blinded observers / interviewers.

STANDARD OF CARE FOR PONV PREVENTION

As per standard of care, all subjects will receive dexamethasone and diphenhydramine intra-operatively for PONV prevention. For patients who fall into the “High Risk for PONV” category (according to departmental standard of care algorithm), anesthesiologist may, at their discretion, consider any of the following: pre-operatively aprepitant; fluid bolus 30ml/kg; Total Intravenous Anesthesia (TIVA); Sub-hypnotic dose propofol of 1mg/kg infused at 20mcg/kg/min.

STUDY PROCEDURES Pre-Operatively, Intra-Operatively and Post-Operatively:

- **Pre-op:** Patients will be consented in clinic whenever possible or on the day of surgery and randomized, with gender stratification. Patients, their families and health care professionals will be blinded as to whether the patient is in the treatment or control group.

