5 STUDY TREATMENTS

5.1 Allocation to Treatment

Subjects will be randomized via previously generated random numbers table and stratifying for female gender.

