9 DATA ANALYSIS/STATISTICAL METHODS

9.1 Sample Size Determination

Anticipating study drug to result in 50% decrease in pruritus from current rate of pruritus for those patients receiving ITM, we need to enroll 56 patients per group to achieve 80% power.

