APPENDIX A – Protocol Algorithm

PATIENTS RECRUITED:

- 3-17 years and ≤ 100 kg
- Scheduled to have low dose intrathecal morphine for orthopedic or urology surgery

Patients randomized to Control or Study group with gender stratification

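### Randomization is stratified by sex, but the planned test of severe pruritus and PONV ignores sex; stratifying the test would be a small, nearly free gain if sex predicts the outcome

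*Combined protocol and SAP*

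**What the plan says.** Three places make sex the stratification factor, and no other factor is named:

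- Section 3, Study Design: "We will recruit 130 children, and randomize using a random numbers table, stratifying for female gender".
- Section 5.1, Allocation to Treatment: "Subjects will be randomized via previously generated random numbers table and stratifying for female gender".
- Appendix A: "Patients randomized to Control or Study group with gender stratification".

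Section 9.2 dichotomizes the outcomes ("Rankings of pruritus and PONV will be coded as none-mild vs. severe"), then states that "Chi-squared and Fishers' Exact tests will be used to compare these outcomes between groups" and that "Significance will be accepted at the 5% level". The Statistical Methods entry of the synopsis has the same text. No section plans a stratified test, a regression model or any other use of sex in the analysis, and no reason is given for leaving it out. The list is described only as a random numbers table; blocking is not mentioned.

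**The concern.** A factor used to restrict randomization is normally carried into the analysis. If the list forces balance within sex and sex predicts pruritus, the difference between arms varies less than an unstratified test assumes. That test uses a standard error that is too large, so it rejects a true null less often than 5% and gives up some power. If the list does not force balance, the unstratified test holds its level, but a stratified test can still remove outcome variation due to sex.

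What is at stake is efficiency only. Power matters here because section 9.1 gives no numerical control rate for its 56 per group, and the only in-house rate in the protocol (40%, section 1.1) implies less than the stated 80%.

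**Working it through.** **Inputs from the protocol.** 56 per group and 80% power (section 9.1); a 50% relative reduction (section 9.1); a 40% in-house pruritus rate, 31 of 77 (section 1.1); 5% significance (section 9.2).

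**Assumptions.** The protocol gives no rates by sex, no female share and no sidedness. I take a two-sided test, an overall placebo rate of 40%, risk halved in each sex, and 56 girls and 56 boys. The difference in placebo rate between the sexes runs from 0 to 40 percentage points.

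**The plan's own figure.** "we need to enroll 56 patients per group to achieve 80% power". With p1 = 0.40, p2 = 0.20 and mean 0.30:

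n = [1.96·√(2·0.30·0.70) + 0.842·√(0.40·0.60 + 0.20·0.80)]² / 0.20² = 81.2, so 82 per group.

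Power at 56 per group is then about 64%. A 50% rate halved gives 58 per group, and 51% gives 56. The sample size is a separate matter; it is shown here only to place the baseline power of about 65% used below.

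**Type I error of the unstratified test under forced balance.** Under the null, the pooled test uses the variance (2/56)·p(1−p) with p = 0.40, so p(1−p) = 0.24. With equal numbers of each sex in both arms, the true variance is (2/56)·v, where v is the mean of p(1−p) over the two sexes. The large-sample error rate is 2·[1 − Φ(1.96/√(v/0.24))]. For 60% in girls and 20% in boys:

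- v = (0.24 + 0.16)/2 = 0.20
- v/0.24 = 0.833, with square root 0.913
- 1.96/0.913 = 2.147, giving 3.2%

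**Simulation.** 1,000,000 trials per scenario, Pearson chi-squared against Cochran-Mantel-Haenszel (CMH), neither with continuity correction. The Monte Carlo standard error of a power near 65% is √(0.65·0.35/1,000,000), about 0.05 points. Power changes come from unrounded values.

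Forced balance, 28 per arm per sex:

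| Placebo rate, girls/boys | Type I error, unstratified: formula | simulated | Power, unstratified | Power, CMH | Change (points) |
|---|---|---|---|---|---|
| 40/40% | 5.0% | 4.7% | 64.9% | 64.7% | -0.3 |
| 45/35% | 4.9% | 4.6% | 64.9% | 64.8% | -0.1 |
| 50/30% | 4.5% | 4.3% | 65.1% | 65.7% | +0.6 |
| 55/25% | 4.0% | 3.7% | 65.4% | 67.2% | +1.8 |
| 60/20% | 3.2% | 2.9% | 65.7% | 69.6% | +3.9 |

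The simulated error lies 0.2 to 0.3 points below the formula throughout, including the row with no sex effect. CMH stays between 4.6% and 5.1%.

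Simple randomization within sex:

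| Placebo rate, girls/boys | Type I error, unstratified | Power, unstratified | Power, CMH | Change (points) |
|---|---|---|---|---|
| 40/40% | 5.1% | 64.5% | 63.7% | -0.8 |
| 45/35% | 5.1% | 64.5% | 64.0% | -0.5 |
| 50/30% | 5.1% | 64.5% | 65.0% | +0.4 |
| 55/25% | 5.1% | 64.5% | 66.4% | +2.0 |
| 60/20% | 5.1% | 64.5% | 68.9% | +4.4 |

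**Sensitivity.**

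- With about 30% girls (34 girls, 78 boys), the changes over the same sex differences are -0.3/-0.1/+0.5/+1.6/+3.3 points under forced balance and -0.8/-0.7/+0.1/+1.4/+3.4 under simple randomization.
- With a 50% placebo rate, forced balance and a common treatment odds ratio, power goes from 79.0% to 78.5% when sex has no effect, from 79.2% to 79.9% at a sex odds ratio of 2, from 79.7% to 81.8% at 3, and from 80.5% to 84.3% at 5 (200,000 trials each). The pattern is the same.
- The protocol gives no PONV rate, so no PONV figure is computed.

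**The case against.** The strongest case against is that nothing is broken. A simple, prespecified, valid test is a legitimate choice. Nothing in the protocol says how strongly sex predicts pruritus or PONV, and at sex differences of 0 or 10 points the stratified test is slightly worse in every scenario. Gains above 1 point need a difference of roughly 30 points. If the list is unrestricted within sex, stratifying the randomization has produced no balance to exploit, and any gain is ordinary covariate adjustment.

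These points stand, and they cap the matter at minor. They do not remove it: the protocol chose sex as its only stratification factor and then left it out of the comparison without a reason, and the possible gain is larger than the possible loss.

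Three limits also stand:

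- Only the Pearson test was simulated, not Fisher's exact test.
- Forced balance was taken as exact, whereas permuted blocks give it only approximately.
- If treatment halves risk in each sex, the risk differences are unequal (30 and 10 points at 60/20%), so a Mantel-Haenszel risk difference is a weighted average rather than a common effect. The CMH test remains valid.

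**Conclusion.** The mismatch between randomization and analysis is real, and minor. It causes no bias and no excess of false positives. Under the assumed 40% placebo rate, halved by treatment, with 56 per arm, stratifying the test changes power by between -0.8 and +4.4 points. The change is under 1 point either way for sex differences up to 20 points. The unstratified test is conservative only if balance within sex is forced and sex is clearly prognostic. The actual gain is unknown, probably small and possibly slightly negative. This is an efficiency refinement that does not threaten the trial's conclusion, and it does not repair any shortfall in sample size.

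**What to change.** In section 9.2 and the matching synopsis entry, name a CMH test stratified by sex as the single primary test for severe pruritus. Report it with the Mantel-Haenszel risk difference and 95% confidence interval, described as an average over the two sexes. Do the same for PONV, and keep exact tests for sparse tables only.

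When section 5.1 is edited, state that the list uses randomly varying permuted blocks within each sex, if that is how it is built. The change to the test is worthwhile without this sentence, but only a restricted list gives the stratification its intended effect.

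The cost is one sentence in each section. No data, staff or patients are added, since sex must be known to randomize. If sex turns out not to matter, the loss is about 0.3 points of power with blocked allocation and about 0.8 points without. The change should be made before any unblinding, including the interim look in section 10.1.

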1.2 Background and Rationale

The mechanism of morphine-induced itch is not fully elucidated. (1, 16, 19). However, neuraxial opioids induce more frequent and intense itch than peripherally administered doses (26). Centrally located Mu-opioid receptors, in the medullary dorsal horn, may play a role, and activation of this site with an opioid injection induced a dose related scratch frequency in primates (23). The mu opioid receptors, but not other opioid receptor subtypes, appear to mediate the neuraxial opioid-induced itch as opposed to intravenously administered opioids (21, 22, 25). However, the physiology is more complex, as morphine induced pruritus is not always reversed with naloxone (13) and effective treatments for neuraxial induced pruritus include partial opioid agonists (1, 13), 5HT3 antagonists (4-7), propofol (13, 24), and prostaglandin modulation (19).

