4 SUBJECT SELECTION

4.1 Subject Recruitment

4.1.1 *Inclusion Criteria*

1. Age: 3-17 years, inclusive and wt </= 100kg
2. Scheduled for any procedure necessitating ITM
3. Ability to use verbal or pictorial pain assessment tools and techniques
4. Informed consent and assent (if applicable)

4.1.2 *Exclusion Criteria*

1. Inability to use verbal or pictorial scoring scales
2. Hypersensitivity to selective 5-HT₃ receptor antagonists

3. Diagnosed congenital long QT syndrome
4. Current use of any medications that prolong QT interval
5. Severe hepatic impairment
6. Pregnancy or nursing mothers
7. Use of serotonin specific reuptake inhibitors within 14 days
8. Use of serotonergic-noradrenergic reuptake inhibitors within 14 days

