6.2 Treatment Study Period

6.2.1 *Day of Surgery through 24 hours post-operative*

Preoperatively, the medical history will be reviewed to confirm that no exclusion criteria have developed since informed consent.

In the operating room, the subject will receive an intra-operative bolus dose of study drug labeled “antipruritic study drug” (ondansetron, 0.1mg/kg or placebo) IV, prior to intrathecal

morphine injection, followed by around-the-clock study drug labeled “antipruritic study drug” (ondansetron doses, of 0.1mg/kg or placebo) IV every 6 hours for 24 hours from OR end time.

Subjects in the operating room, recovery room, and PACU will be monitored as per standard clinical care.

Data collection

For the first 24 hours after surgery, subjects will be visited in the Post Anesthesia Care Unit (PACU), the evening of surgery, the next morning and at 24 hours postoperatively (not between the hours of 10p-7a) to obtain the presence and degree of adverse effects, our primary outcomes. Pruritus will be scored similar to previous pediatric studies, as 0 = none; 1 = mild/tolerable/not requiring treatment; 2 = severe/intolerable/requiring treatment (12). We will use a similar method to quantify the amount of nausea/vomiting each patient experiences (0 = no nausea/vomiting; 1 = mild/tolerable nausea/vomiting not requiring treatment; 2 = severe/intolerable nausea/vomiting requiring treatment) (14). The following data will also be collected: all analgesics, antiemetic, and antipruritic agents used.

SCHEDULE OF ACTIVITIES

Protocol Activity	Screen	Day of surgery	Follow-up: OR end +24 hrs
Informed Consent	X		
Review of medical history	X	X	
Vitals	X	X	
Randomization		X	
Treatment with study agent		X	X
Pruritus and PONV assessment			X
Adverse Event Assessment		X	X
Concomitant Medication	X	X	X

Note: Pregnancy test is performed as standard of care for all post-menarcheal females scheduled for surgery at C. Mott Children's Hospital.

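### Section 9.2 tests severe pruritus only with unadjusted 2x2 tests; prespecified adjustment for age and sex would be a modest gain in efficiency and robustness

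*Combined protocol and SAP*

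**What the plan says.** The whole analysis of the primary outcome is in section 9.2 and is repeated in the synopsis. "Rankings of pruritus and PONV will be coded as none-mild vs. severe", after which "Chi-squared and Fishers' Exact tests will be used to compare these outcomes between groups". "Significance will be accepted at the 5% level"; whether this is one- or two-sided is not stated. No regression, stratified test or covariate appears anywhere. The same section plans t tests or Mann-Whitney tests for continuous data, but no continuous endpoint is defined.

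Sections 3 and 5.1 stratify the randomization by sex only, and section 9.2 does not use that stratum. Age (3-17 years) and weight are eligibility criteria in section 4.1.1, so both are known before allocation. For drug data, section 6.2.1 says: "The following data will also be collected: all analgesics, antiemetic, and antipruritic agents used".

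**The concern.** Children of 3 and of 17 may well differ in their risk of reaching the severe grade, or in how they report it. Nothing in the design balances age between arms. A 2x2 test leaves any such difference in risk as noise and does not correct an imbalance that arises by chance.

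The protocol gives some reason to expect risk to vary. Section 1.1 describes pruritus "with a reported incidence of 30-70" per cent, and section 1.2 reports that "activation of this site with an opioid injection induced a dose related scratch frequency in primates". Eligibility is broad ("Scheduled for any procedure necessitating ITM"), although Appendix A narrows it to orthopedic and urologic operations.

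At stake is some power in a trial that has little to spare, and the ease with which a result could be challenged if the arms differed in age.

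**Working it through.** **Inputs**
- Sample size: section 9.1 says "we need to enroll 56 patients per group to achieve 80% power", for a 50% reduction from a current rate that it does not state.
- Control rate: 31/77 = 40.3% in section 1.1. This is the share needing anti-pruritic treatment, so it corresponds to the severe grade. Taken as 40% against 20%.
- Level: 5%, assumed two-sided.
- Prognostic strength of age: not in the documents. Assumed odds ratios (OR) of 1, 1.5, 2 and 3 per standard deviation (SD).

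**1. The plan's own figure**

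n per arm = [1.96 √(2p̄q̄) + 0.842 √(p₁q₁ + p₂q₂)]² / (p₁ − p₂)²

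At 40% against 20%, p̄ = 0.30:
- 1.96 × √0.42 = 1.270 and 0.842 × √0.40 = 0.532.
- (1.802)² / 0.04 = 81.2, so 82 per arm, not 56.

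Power at 56 per arm is Φ[(0.20 × √56 − 1.270) / 0.632] = Φ(0.36) = 64%. Exact enumeration gives 65% for chi-squared and 57% for Fisher. The figure of 56 is reached with a control rate near 51%, a rate the documents do not name; 50% gives 58.

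**2. Power with and without adjustment**

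Simulation at 56 per arm: severe pruritus follows a logistic model in arm and a standard-normal covariate, with marginal rates held at 40% and 20%. The unadjusted chi-squared test is compared with the likelihood-ratio test for arm in the adjusted model.

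| Assumed OR per SD | Unadjusted | One covariate | Two covariates, at most one prognostic |
|---|---|---|---|
| 1 | 65% | about 65% | 65.5% |
| 1.5 | 65% | 66-67% | 66.5% |
| 2 | 65% | 69% | 69.2% |
| 3 | 65% | 73% | not run |

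An extreme covariate (log-odds 1.5 per SD, OR about 4.5) gives 78%.

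A stratified (Cochran-Mantel-Haenszel) test with two equal strata averaging 40% in controls, each halved by treatment, shows the same pattern. Control rates of 30% and 50% give 64.9% rising to 65.3%; 20% and 60% give 64.8% rising to 69.0%.

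If the control rate were 50% (against 25%), unadjusted power is 78-80%. Adjusted power is then 80%, 81%, 87% and 90% at log-odds of 0, 0.5, 1.0 and 1.5 per SD.

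**3. Type I error**

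The unadjusted test holds its level (4.3-5.2%). The adjusted likelihood-ratio test gave 4.8-5.8% with one covariate (2,000 null runs per setting). With two covariates it gave 5.3-5.7% in one set of runs and about 5.0-6.3% in another.

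**4. Chance imbalance**

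The standardised difference in a covariate between arms has standard error √(2/56) = 0.189. About 1 trial in 20 therefore exceeds 1.96 × 0.189 = 0.37 SD in one direction or the other. At an imbalance of that size the unadjusted odds ratio moves by a factor of about 1.5^0.37 = 1.16, 2^0.37 = 1.29 or 3^0.37 = 1.50 for the three non-null assumptions.

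**5. Can the data carry the model?**

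Expected events are 56 × 0.40 + 56 × 0.20 = 22.4 + 11.2 = 33.6. For arm, age and sex that is 33.6 / 3 = 11.2 events per coefficient.

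**The case against.** The case for leaving section 9.2 alone is substantial. Randomization makes the unadjusted test valid, and its 5% level already allows for chance imbalance. No passage says that age predicts pruritus in these children. The primate finding concerns opioid injected at one brainstem site. The 30-70% range runs across reports and could reflect differing definitions or populations. At a modest odds ratio of 1.5 the gain is 1 to 2 points, and part of that may come from the adjusted test being slightly liberal. All of this stands. It limits the point to an improvement but does not remove it: with a covariate of no value simulated power did not fall, and the change needs no extra patients. The planned t test or Mann-Whitney test could display an age imbalance but would not correct for it.

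Two stronger readings are tempting.

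- **A reader might infer that intrathecal morphine dose, the direct cause of the outcome, varies widely, is already recorded and should be in the model.** The documents do not show this. No dose or range is given, and Appendix A calls it only low. Section 6.2.1 lists analgesic agents without naming the intrathecal dose as a data item. Section 3 places the injection after randomization and after the first study dose, so the given dose is not strictly a baseline value. Blinding of the medical team makes dependence on allocation unlikely, but a planned dose recorded beforehand would be cleaner.
- **A reader might infer that adjustment would repair the power.** It would not. At 40% against 20% about 82 per arm are needed, and every covariate strength tried leaves power below 80%.

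**Conclusion.** The point holds as a low-cost improvement in efficiency and robustness. The plan ignores a baseline variable that it has for every child, and leaves out of the analysis the one factor it stratifies on. At the site's own 40% rate, adjustment is worth between nothing and about 8 points of power (65% to 73%) for odds ratios of 1 to 3 per SD. It also protects against an age imbalance that could shift the odds ratio by a factor of about 1.2 to 1.5 in the least balanced 1 trial in 20.

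That adjustment does little harm is well supported. The size of the benefit is not, because it rests wholly on an assumed prognostic strength, on 56 analysed per arm, on a two-sided 5% level and on rates of 40% against 20%.

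**What to change.** In section 9.2 and the synopsis, prespecify that:
- the primary comparison is a logistic regression of severe pruritus on arm, adjusted for age in years (continuous) and for sex as the stratification factor;
- the result is reported as a standardised risk difference (predicted risks averaged over all children under each arm) with its 95% CI, stating the test, its sidedness and which result decides significance;
- the unadjusted chi-squared or Fisher test is kept as a sensitivity analysis.

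Add intrathecal morphine dose (mcg/kg) as a covariate only if the planned dose is made a named item on the case report form and recorded before randomization.

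Make the change before any unblinding. Section 10.1 has the statistician break the blind at 20 patients per group, so it should be settled before then.

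The cost is a paragraph of text, with no added patients or procedures. The downsides are a primary result that depends on a model instead of a plain 2x2 table, and a likelihood-ratio test that is slightly liberal at this sample size (about 5-6%). The shortfall against 80% power needs its own remedy.
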